7.9.3.3. Exclusion of Thoracic Lesions

Rate of exclusion of thoracic lesions will be reported for 1-month, 6-month and each annual follow-up. The endpoints may be analyzed using site-reported imaging assessments or core lab reported imaging assessments, separately.

Revision [6.0]

Page 21 of 27

Exclusion of Aneurysm

Exclusion of Aneurysm is defined as the absence of a type I or III endoleak associated with the absence of growth of > 5 mm of the maximum measurable aneurysm diameter; reference diameter is the diameter measured at first post-operative imaging exam.

Rate of Exclusion of Aneurysm will be calculated for each scheduled follow-up and the calculation will be based on the number of subjects who had the event divided by number of implanted subjects that are evaluated for that event at the time point. Imaging endpoint analysis time windows will be used to determine if an image assessment belongs to a respective time point. The reporting details can be found in Section 7.2.3 (Table 1).

The endpoint will be derived as follows:

- Subjects having a Type I or III endoleak or having aneurysm growth > 5mm will be considered as failures of the endpoint [defined as k].
- Otherwise subjects without a failure event and having evaluable imaging for both endoleak and aneurysm growth will be considered as a success (i.e. Exclusion of the aneurysm) [defind as m].
- Subjects without a type I or III endoleak and without aneurysm growth > 5mm, but missing one or both imaging assessments will be excluded from the analysis.

The rate will be calculated as m/(m+k), where the numerator will consist of all subjects having success for exclusion of the aneurysm [m]. The denominator will consist of all subjects having exclusion [m] or subjects having a failure event [k].

[figure not shown]
The endoleak component will be derived according to Section 7.9.3.5.

The aneurysm growth component is based on the calculated difference between the assessments at follow-up minus the first post-operative assessment. Subjects must have the maximum aneurysm diameter reported at both the post-operative assessment and the follow-up assessment. If the subject is missing either the post-operative and/or follow-up assessment, the subject is considered to have missing data for this component. The post-operative image can be either at 1 month follow-up or discharge. At each follow-up the largest aneurysm diameter will be used in the calculation of aneurysm diameter change from baseline.

Scenarios for each possible combination of the component outcomes and the final endpoint assessment of success vs. failure are presented in Table 4. Since the exclusion of aneurysm is an assessment of success with two component events, if both component events are 'success' then the final composite endpoint will be 'success' (scenario 1); if at least one component event is 'failure' then the final composite endpoint is 'failure' (scenario 2,3,4,5 8); if one component event is success, but the other component event is missing due to unevaluable data, the final composite endpoint will be missing

Revision [6.0]

Page 22 of 27

(scenario 6,7); finally, if both components are missing then composite endpoint will be missing (scenario 9):

Table 4. Exclusion of Thoracic Lesion Scenarios

	1 st component	2 nd component even	Composite		
Scenarios	Absence of Type I or III Endoleak	1 st post-operative assessment of Maximum aneurysm/dissectio n/PAU diameter	assessment of Maximum aneurysm/dissection /PAU diameter at each scheduled visit	Absence of growth > 5 mm	endpoint of Exclusion of TAA/PAU
1	Success	evaluable	evaluable	Success	Success
2	Success	evaluable	evaluable	Failure	Failure
3	Failure	evaluable	evaluable	Success	Failure
4	Failure	evaluable	evaluable	Failure	Failure
5	Missing	evaluable	evaluable	Failure	Failure
6	Missing	evaluable	evaluable	Success	Missing
7	Success	Missing/evaluable	Evaluable/missing	Missing	Missing
8	Failure	Missing/evaluable	Evaluable/missing	Missing	Failure
9	Missing	Missing/evaluable	Evaluable/missing	Missing	Missing

Exclusion of Penetrating Aortic Ulcer (PAU)

Exclusion of penetrating aortic ulcer (PAU) is defined as the absence of a type I or III endoleak associated to the absence of growth > 5 mm of the maximum measurable aortic diameter at the level of PAU; the reference diameter is the diameter measured at the first post-operative imaging exam.

The rate of the exclusion of PAU will be calculated similarly to that of the exclusion of Aneurysm;

Exclusion of False Lumen (dissection)

Exclusion of false lumen (dissection) is defined as the exclusion of primary entry tear of dissection associated to the thrombosis of false lumen at the level of stent graft.

Rate of exclusion of Dissection will be calculated at the post-operative time point and at each scheduled follow-up and the calculation will be based on the number of subjects who had the event divided by the number of implanted subjects under the Dissection indication who are evaluated for that event at the time point. The imaging endpoint analysis time window will be used to determine if an image assessment belongs to a respective time point and the reporting details can be found in section 7.2.3 (Table 1).

Revision [6.0]

Page 23 of 27

Form Medtronic

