 - Aortic remodeling post-procedure as measured by:
 - Change from baseline* in the maximum true lumen (TL) diameter over the length of the stent graft
 - Change from baseline* in the maximum false lumen (FL) diameter over the length of the stent graft
 - Change from baseline* in the maximum total descending thoracic aortic
 - FL thrombosis over the length of the stent graft

VML_Eval Statistical Analysis Plan	Form
Revision [6.0] Page 8 of 27	Medtronic

^{*} The discharge computerized tomography angiogram (CTA) will be used as baseline to assess aortic changes. If a discharge CTA is not performed then, the one month follow-up CTA will be used for baseline purposes.

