7.9.3.2. Aneurysm Diameter Changes

Aneurysm Diameter change will be calculated based on the maximum measurable aneurysm diameter during the post-operative follow-up and each annual follow-up. Reference diameter is the diameter measured at first post-operative follow-up through 1 month. Change of aneurysm diameter will be defined as 1) "increased" if an aneurysm growth is strictly greater than 5 mm of the maximum measurable aneurysm diameter; 2) "decreased" when an aneurysm becomes strictly smaller in size by more than 5 mm; 3) "no change" when the change is within 5 mm.

[figure not shown]
Aneurysm diameter change rates will be calculated separately for increase, decrease and no change based on the number of subjects who had the event divided by number of implanted subjects who are evaluated for aneurysm diameter change at the time point. The analysis time window will be used to determine if an image assessment belongs to a respective time point. The analysis time window for each time point is given in Section 7.2.3.

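### In the lesion-exclusion rate (SAP 7.9.3.3), a subject with one component unevaluable can count only as a failure, so m/(m+k) is biased low even when images are missing completely at random

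*SAP*

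**What the plan says.** SAP 7.9.3.3 defines exclusion of the aneurysm as no type I or III endoleak together with no growth above 5 mm. For the comparison diameter, "reference diameter is the diameter measured at first post-operative imaging exam". The section then narrows which image may serve: "The post-operative image can be either at 1 month follow-up or discharge". SAP 7.9.3.2 sets the same limit for diameter change: "Reference diameter is the diameter measured at first post-operative follow-up through 1 month". The footnote to the additional observations in 4.3.3, repeated in 7.9.3.4, gives one fallback only: "If a discharge CTA is not performed then, the one month follow-up CTA will be used for baseline purposes". No section allows a later reference, and 7.4 rules out imputation in general.

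On missing data, 7.9.3.3 says: "Subjects must have the maximum aneurysm diameter reported at both the post-operative assessment and the follow-up assessment". It continues: "If the subject is missing either the post-operative and/or follow-up assessment, the subject is considered to have missing data for this component". Subjects with no failure observed "but missing one or both imaging assessments will be excluded from the analysis". The text above Table 4 repeats the rule: "if one component event is success, but the other component event is missing due to unevaluable data, the final composite endpoint will be missing". A failure on either component settles the composite as a failure, whatever the state of the other.

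The rate is m/(m+k), with m successes and k failures, at 1 month, 6 months and yearly to 5 years. Penetrating ulcer is handled in the same way.

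**The concern.** Success needs both components to be evaluable; failure needs only one. That is sensible for labelling a single subject, but the denominator is built from the labels. Among partly evaluated subjects, those whose one known component is bad stay in and those whose one known component is good leave. Whether a subject is counted therefore depends on the outcome being estimated, and random loss of images does not average this out.

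Two routes lead there. In the first, growth is missing because the reference or the follow-up diameter is missing. If the reference is missing, the gap is permanent. In the second, endoleak is unevaluable. Table 2 marks CTA or MR without contrast as adequate for aneurysm size but not for endoleak, so one such scan is enough if it is the only image in the window.

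At stake is how the five-year series is read. If image completeness changes from visit to visit, part of any change in the exclusion rate may reflect the images rather than the device. The SAP says the data may be used in marketing applications (4.2).

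**Working it through.** **Step 1: the rules against Table 4.** The text reduces to three rules: any failed component gives Failure; two successes give Success; anything else gives Missing. These reproduce all nine rows of Table 4.

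**Step 2: what a partly evaluable subject can reach.**

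| State | Known component good | Known component bad |
|---|---|---|
| Growth missing | Scenario 7: Missing, dropped | Scenario 8: Failure, in k |
| Endoleak unevaluable | Scenario 6: Missing, dropped | Scenario 5: Failure, in k |

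With both missing (scenario 9) the subject is dropped. Scenario 1 is the only route to m. A subject with no reference diameter can reach only scenarios 7, 8 and 9, and this holds at 6, 12, 24, 36, 48 and 60 months however complete the later scans are.

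**Step 3: who lacks a reference.** In Table 1 the imaging analysis windows are days 1-14 for discharge and days 15-122 for 1 month. The reference is lost only if no image on days 1-122 yields a diameter.

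**Step 4: expected rate.** The plan states no figure for this endpoint, so every input here is an assumption. Let r be the share without a reference, q the share with growth but not endoleak evaluable, a the endoleak risk and g the growth risk. Endoleak, growth and missingness are taken as independent.

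- True rate: (1-a)(1-g)
- Expected SAP rate: (1-q-r)(1-a)(1-g) / [(1-q-r) + qg + ra]
- Rate in scenarios 1-4 only: (1-q-r)(1-a)(1-g)/(1-q-r) = (1-a)(1-g), which is unbiased

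| r | q | a | g | True | SAP rate | Shift (points) |
|---|---|---|---|---|---|---|
| 5% | 0 | 5% | 20% | 76.0% | 0.95×0.76/0.9525 = 75.8% | -0.2 |
| 11% | 0 | 5% | 20% | 76.0% | 0.89×0.76/0.8955 = 75.5% | -0.5 |
| 20% | 0 | 10% | 5% | 85.5% | 0.80×0.855/0.82 = 83.4% | -2.1 |
| 11% | 10% | 5% | 5% | 90.25% | 0.79×0.9025/0.8005 = 89.1% | -1.2 |
| 11% | 20% | 5% | 20% | 76.0% | 0.69×0.76/0.7355 = 71.3% | -4.7 |
| 11% | 30% | 10% | 20% | 72.0% | 0.59×0.72/0.661 = 64.3% | -7.7 |

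The first and third rows are the ends of the range for a missing reference alone (r 5-20%, a 5-10%, g 5-20%). The fourth and sixth are the ends with q at 10-30% and r at 11%. In the fifth row most of the shift comes from unevaluable endoleak: r alone gives -0.5, while q = 20% alone gives 0.80×0.76/0.84 = 72.4%, or -3.6.

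**Step 5: an illustrative count (assumed).** Take 23 TAA/PAU subjects. Of these, 20 have both components evaluable (18 successes, 2 failures) and 3 have no reference (1 endoleak, 2 none).

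- SAP rule: 18/21 = 85.7% (exact 95% CI 63.7-97.0%)
- Both components evaluable: 18/20 = 90.0% (68.3-98.8%)
- Bounds with the two scenario 7 subjects as failures or as successes: 18/23 = 78.3% to 20/23 = 87.0%

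The 90.0% lies above the upper bound because it leaves out an observed endoleak.

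**The case against.** The strongest defence is that the rule is deliberate and visible. One failed component does settle the composite, and the SAP sets out all nine combinations. The error understates success. The study tests no hypotheses, and exclusion is one of many additional observations. Endoleak and diameter change are also reported separately, 7.1.1.2 tabulates image adequacy by visit, and 7.4 lists missing endpoint data by subject. For a missing reference alone, the shift is at most about 2 points, under half of one subject in an assumed 23 (1/23 = 4.3 points).

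Most of this stands and limits the weight of the point. It does not remove the bias: listings and separate component rates do not correct m/(m+k). The worst-case principle in 7.2.3 and 7.12 governs which finding is used within a window; it does not address missing components.

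A reader might infer more than the documents support:

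- That one missed early scan costs five years of data. It does not, because any diameter on days 1-122 can serve.
- That the 8/9 with a maximum diameter at 1 month in the 7.1.1.2 example table is evidence for r = 11%. It is a table example for one visit, and a discharge image could still supply the reference.
- That this is the SAP's main long-term effectiveness measure, or that the bias carries into 30-day treatment success. The SAP does not call it that, and 7.9.2 does not say it uses this derivation.

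**Conclusion.** The point holds. For aneurysm and penetrating ulcer, m/(m+k) keeps partly evaluated failures and drops partly evaluated non-failures, so it is biased low whenever some subjects have only one component evaluable and failures occur. A missing reference diameter makes this permanent for the subject concerned.

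The size is unknown from the documents, which give neither the share of incomplete images nor the event risks. The ranges in the working rest on assumed, independent rates, and the upper end needs endoleak to be unevaluable in 30% of subjects. They also leave out endoleaks known only through an intervention, which 7.9.3.5 counts without an image.

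The effect is conservative, confined to a descriptive additional observation, and modest unless unevaluable images are common. False-lumen exclusion is not affected: it has its own definition, although a Table 4 column heading mentions dissection. The available protocol pages carry no readable text on the endpoint, so whether the protocol itself fixes the post-operative baseline could not be checked.

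**What to change.** Keep m/(m+k) as defined. In 7.9.3.3, add three items to be shown beside it at each visit for aneurysm and penetrating ulcer:

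- (a) the exclusion rate among subjects with both components evaluable (scenarios 1-4), which is unbiased if missingness is completely at random;
- (b) the number of subjects in each of scenarios 5 to 9, and how many lack a reference diameter;
- (c) bounds with scenarios 6 and 7 counted all as success and then all as failure.

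The cost is a few lines of SAP text and slightly more tabulation, from data already collected. Rate (a) leaves out the observed failures in scenarios 5 and 8, so it should accompany m/(m+k) and not replace it.

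The baseline need not change. A later scan as reference would hide earlier growth, so it should be at most an optional, flagged sensitivity analysis. A pre-implant reference is not advised, because it departs from the SAP's post-operative baseline.

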7.9.3.4. Additional Dissection Specific Assessments

Additional dissection specific assessments include the following:

- Coverage of primary entry tear (exclusion of false lumen)
- Extension of dissection (proximally or distally) with or without complications
- Continuing or new false lumen (FL) perfusion
 - Primary intimal tear false lumen perfusion (PIT FLP)
 - Proximal aorta false lumen perfusion (PA FLP)
 - Distal aorta false lumen perfusion (DA FLP)
 - Proximal branch false lumen perfusion (PB FLP)
 - Distal branch false lumen perfusion (DB FLP)
- Aortic remodeling post-procedure as measured by:
 - o Change from baseline* in the maximum true lumen (TL) diameter over the length of the stent graft
 - Change from baseline* in the maximum false lumen (FL) diameter over the length of the stent graft
 - o Change from baseline* in the maximum total descending thoracic aortic diameter
 - FL thrombosis over the length of the stent graft
 - * The discharge computerized tomography angiogram (CTA) will be used as the baseline to assess aortic changes. If a discharge CTA is not performed then, the one month follow-up CTA will be used for baseline purposes.

The rate of the above endpoints will be calculated at the post-operative time point and at each scheduled follow-up and the calculation will be based on the number of subjects who had the event divided by number of implanted subjects under the Dissection indication who are evaluated for that event at the time point. The imaging endpoint analysis time window will be used to determine if an image assessment belongs to a respective time point and the reporting details can be found in section 7.2.3 (Table 1).

Thoracic dissection measurement over entire DTA and thoracic measures over endograft segment

If there are multiple images in a reporting window, the image with the largest maximum thoracic aortic centerline diameter over the entire DTA in the window will be used for reporting all related measurements (e.g., maximum thoracic aortic centerline diameter, maximum true lumen diameter, etc.)

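### An aneurysm or ulcer subject whose only post-operative scan is the 1-month scan is compared with itself, so 1-month growth passes automatically

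*SAP*

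**What the plan says.** **Reference image.** For aneurysm diameter change, SAP 7.9.3.2 states: "Reference diameter is the diameter measured at first post-operative follow-up through 1 month". For exclusion of aneurysm, 7.9.3.3 states "reference diameter is the diameter measured at first post-operative imaging exam" and adds "The post-operative image can be either at 1 month follow-up or discharge". Exclusion of a penetrating ulcer uses the same kind of reference. For dissection remodeling, the baseline is the discharge CTA, with a fallback: "If a discharge CTA is not performed then, the one month follow-up CTA will be used for baseline purposes" (7.9.3.4). The footnote to 4.3.3 repeats that fallback and attaches it to aneurysm diameter change as well.

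**Comparison.** Growth is the "calculated difference between the assessments at follow-up minus the first post-operative assessment", and "At each follow-up the largest aneurysm diameter will be used in the calculation of aneurysm diameter change from baseline" (7.9.3.3). A diameter is needed at both assessments, otherwise the growth component is missing. Nothing says that the two must come from different images.

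**Time points.** "Rate of exclusion of thoracic lesions will be reported for 1-month, 6-month and each annual follow-up" (7.9.3.3). Section 4.3.3 places diameter change among the observations evaluated through the 30 day visit. Section 7.9.3.4 reports the dissection measures at the post-operative time point and at each scheduled follow-up.

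**Windows.** In Table 1 the discharge imaging window is Days 1-14 and the 1-month window is Days 15-122. When a window holds several dissection images, "the image with the largest maximum thoracic aortic centerline diameter over the entire DTA in the window will be used" (7.9.3.4).

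**The concern.** The plan lets the 1-month image be the reference and also reports a change at 1 month. For a subject with a single post-operative image, the two values are then the same number. That subject enters the 1-month tables as evaluated and unchanged, and as a growth success in the exclusion endpoint (Table 4, scenario 1), although nothing was compared.

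This would dilute the 1-month rates of increase and decrease, inflate the no-change rate, and leave 1-month exclusion in these subjects resting on the endoleak finding alone, although its definition has two components. The case is foreseeable: the SAP writes a fallback for it, and Table 1 gives discharge no target day and no scheduled window.

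**Working it through.** The plan states no figure on this point, so there is none to reproduce. The check applies its rules to worked cases and then sizes the effect.

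**1. Aneurysm or ulcer at 1 month.** Change = largest diameter in Days 15-122 minus first post-operative diameter (7.9.3.3). The diameters below are invented.

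| Earlier image | Scans in Days 15-122, in order | 1-month change | Class (5 mm limit, 7.9.3.2) |
|---|---|---|---|
| none | 60 | 60 - 60 = 0 | no change; growth passes |
| none | 60, 67 | 67 - 60 = +7 | increased; growth fails |
| none | 67, 60 | 67 - 67 = 0 | no change; growth passes |
| 60 | 67 | 67 - 60 = +7 | increased; growth fails |
| 67 | 60 | 60 - 67 = -7 | decreased; growth passes |

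Zero is forced only in the first row. With no earlier image and several scans, the result is the largest minus the first. It can be positive but never negative, so a decrease cannot be recorded at 1 month.

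**2. Dilution of the increase rate.** Let f be the share with a single post-operative image among subjects evaluated for the measure, and g the rate of growth above 5 mm among the others. Reported rate = (1 - f) x g. With g assumed to be 10%, it is 10%, 7.5%, 5.0%, 2.5% and 0% for f = 0, 25, 50, 75 and 100%.

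In counts: up to 44 subjects are planned, with a minimum of about 25% for dissections (4.2), which leaves at most about 44 x 0.75 = 33 aneurysm or ulcer subjects. If 11 of 33 had a single image (f = 1/3) and 2 of the other 22 grew, the table would show 2/33 = 6.1% instead of 2/22 = 9.1%.

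**3. Coding the growth component as missing instead.** Table 4 then drops an endoleak-free subject (scenario 7) but keeps a subject with a type I or III endoleak as a failure (scenario 8). Let e be the endoleak rate, assumed independent of growth and equal in both groups.

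- Self-comparison: exclusion rate = (1 - e)(1 - (1 - f)g)
- Missing: exclusion rate = (1 - f)(1 - e)(1 - g) / ((1 - f) + f e)
- Comparable subjects only: (1 - e)(1 - g)

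With g = 10% and e = 5% or 10%, all assumed:

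| f | Self-comparison, e = 5% / 10% | Missing, e = 5% / 10% | Comparable only, e = 5% / 10% |
|---|---|---|---|
| 25% | 87.9% / 83.3% | 84.1% / 78.4% | 85.5% / 81.0% |
| 50% | 90.3% / 85.5% | 81.4% / 73.6% | 85.5% / 81.0% |
| 75% | 92.6% / 87.8% | 74.3% / 62.3% | 85.5% / 81.0% |

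For example, at f = 50% and e = 10%: 0.90 x (1 - 0.05) = 85.5% for self-comparison, and 0.405 / 0.55 = 73.6% for missing. The first reading errs upward and the second downward.

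**4. Dissection remodeling.** With no discharge CTA and one scan in Days 15-122, baseline and 1-month value are the same scan, so every 1-month diameter change is 0.

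With two or more CTs in that window, 7.9.3.4 does not say which one is the baseline. If the largest-image rule chose it, total aortic diameters of 60 and 67 mm in either order would give a baseline of 67 mm and a 1-month change of 0. Later change would also start too high. With two baseline scans, one later scan, no true change and normal measurement error, the mean apparent change is -SD/sqrt(pi), that is -0.56, -1.13 and -1.69 mm for an assumed per-scan SD of 1, 2 and 3 mm. With the first scan as baseline it is 0.

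**5. Path to primary effectiveness.** Section 7.9.2 requires exclusion of the aneurysm at the 30 day visit but does not cite 7.9.3.3. Section 4.3.2 names the ulcer and, for dissections, the primary entry tear. Exclusion of false lumen in 7.9.3.3 has no growth component.

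**The case against.** The strongest reply is that 7.9.3.3 asks for a diameter at both the post-operative and the follow-up assessment. Two separately named assessments can fairly be read as two images, which would make a single-image subject missing. That reading is open, but the SAP does not state it, and step 3 shows that it replaces an upward distortion with a downward one.

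Several stronger conclusions that a reader might draw are not supported:

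- *That 1-month change is zero whenever there is no discharge CTA.* For aneurysms and ulcers, 7.9.3.3 sets the first exam against the largest follow-up diameter, so several scans can show growth and fail the endpoint. The condition there is also no earlier evaluable image of any qualifying type: Table 2 accepts MR for size.
- *That the largest scan becomes the dissection baseline.* The rule speaks of reporting windows and does not mention baseline selection. Because it selects on total aortic diameter, the chosen image need not have the largest true or false lumen.
- *That the primary endpoint is compromised.* The link to 7.9.3.3 is not stated, growth cannot reach dissection subjects by this route, and aneurysm or ulcer subjects can still fail on endoleak.
- *That rates shrink by the share without a discharge CTA, over all 44 subjects.* The relevant share has a single image among those evaluated for the measure, and the no-change rate rises.

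It also stands that the study is descriptive, with no hypothesis tests, and that aneurysm and ulcer change from 6 months onward keeps a valid reference, because the first exam is named.

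**Conclusion.** The point holds for aneurysm and ulcer subjects with no earlier evaluable post-operative image and exactly one scan in Days 15-122. On the literal text their 1-month change is zero and their growth component passes with nothing compared. The same self-comparison affects 1-month dissection remodeling in single-scan subjects without a discharge CTA. Neither available reading gives a sound 1-month exclusion rate, so this is more than a missing detail.

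The size is unknown, because the documents available do not give the single-image share. The reported increase rate is (1 - f) times the comparable rate; the 10% growth rate and the 5% and 10% endoleak rates above are assumptions. Any effect on primary effectiveness is conditional on treatment success using the 7.9.3.3 derivation, and is confined to aneurysm and ulcer subjects. The dissection baseline is an ambiguity to close: later total aortic growth would be understated only if the largest-image rule were applied to the baseline window, and only in subjects with two or more CTs there and no discharge CTA.

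**What to change.** (a) In 7.9.3.2 to 7.9.3.4, count a subject for change or growth at a visit only if the follow-up image is later than, and different from, the reference image. At 1 month, show single-image subjects as growth not assessable, with their count. Beside the two-component exclusion rate, report 1-month absence of type I or III endoleak for every subject with evaluable endoleak imaging, so that endoleak failures and successes are treated alike.

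(b) In 7.9.3.4, state that the largest-image rule does not select the dissection baseline, which is the earliest evaluable post-operative CTA. First-exam wording already applies to aneurysms and ulcers. Reconcile it with the 4.3.3 footnote, which names a discharge CTA where 7.9.3.3 says imaging exam.

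The cost is a few SAP sentences and no new data. The downside is a smaller denominator for 1-month change.
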